### 9.2 Secondary study parameters

The categorical data will be summarized by the frequencies and percentages and tested within the group between baseline and 3 months using a Pearson's Chi-squared test. The continuous data will be summarized in mean with standard deviation in case of normal distribution or median with interquartile range in case of non-normal distribution. A paired two-tailed Student's t test or Wilcoxon signed rank test will be used to calculate the effect within the group between baseline and 3 months.

Differences in outcomes between the groups (diet vs placebo and supplement vs placebo) will be tested with a Student's t test for normally distributed data or Mann-Whitney *U* test for non-normally distributed data.

A paired two-tailed Student's t test or Wilcoxon signed rank test for differences of the primary and secondary parameters between baseline and 6 months within the group will be used to evaluate the legacy effect of the interventions 3 months after stopping with the intervention.

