## 2. OBJECTIVES

Primary Objective:

1. To investigate whether a fasting mimicking diet improves the Microvascular Health Index between baseline and 3 months in type 2 diabetic South Asian patients with microalbuminuria in comparison to the placebo group.
2. To investigate whether intervention with the food supplement Endocalyx™ improves the Microvascular Health Index between baseline and 3 months in type 2 diabetic South Asian patients with microalbuminuria in comparison to the placebo group.

Secondary Objectives:

If the fasting mimicking diet and the food supplement after 3 months can:

[figure not shown]
- Decrease inflammation (urinary heparanase and MCP-1 expression, serum CRP and MCP-1 levels).
- Reduce occurrence of specific urinary HS domains.
- Reduce albuminuria
- Improve metabolic parameters; fasting glucose, HbA1c, C-peptide, IGF-1, total cholesterol, LDL cholesterol, HDL cholesterol, and triglycerides serum levels, waist circumference, waist-to-hip ratio, body weight and systolic blood pressure.

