## Urine collection

The first morning urine of the day will be collected on the day of the study visit. Levels of creatinine, albumin, heparanase, MCP-1 and HS-fragments will be measured in the urine samples. The presence of leukocytes or nitrite in the urine will be tested with a dipstick. In the FMD arm, urinary ketones will be measured after the first 5 days of the first cycle to assess the compliance of the patients. Analysis of the urine samples will be done in the LUMC and Radboud University Medical Center. The urine samples will be stored in the LUMC.

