### **SDF imaging**

Sidestream dark field (SDF) imaging is a non-invasive technique that measures the endothelial glycocalyx with a handheld camera that visualizes the sublingual microvasculature. The CE-marked camera is put under the tongue of the patients and measures in total about 3000 vascular segments in the sublingual vessels. The investigator moves the camera to a different location in the mouth until the total amount of frames necessary is determined automatically. This takes about 2-4 minutes.

The camera uses green LED light to detect the hemoglobin in red blood cells and measures lateral red blood cell (RBC) movements, RBC filling percentage, vessel density, and local vascular perfusion efficiency. These parameters reflect the endothelial glycocalyx health status and are affected if the glycocalyx layer is impaired [32, 33]. The image acquisition is automatically mediated through the Glycocheck software (Glycocheck BV, Maastricht, the Netherlands), which combines these parameters and calculates the Microvascular Health Index (MHI). This index ranges from 0.00 to 10.00 with a score between 0.00 – 1.00 reflecting a clinically perturbed glycocalyx and perfusion in the microvasculature, a score between 1.00 – 2.00 a less than average health of the microvasculature, 2.00 – 3.00 an average microvascular health, between 3.00 and 5.00 an above average and a score above 5.00 a good functional microcirculation with adequate endothelial glycocalyx coverage and flow mediated adaptation.

In addition, capillary tortuosity will be determined by placing the SDF camera in four quadrants of the inner lip (duration about 1-2 minutes): the upper right quadrant, upper left quadrant, lower right quadrant and lower left quadrant. From these collected frames, the

capillary tortuosity will be assessed by scoring the number of twists per capillary in the capillaries in the field of view per image. The number of twists will be stratified as 0: no twists (or pinhead capillaries) to 4: four or more twists, described by Djaberi et al. [53] The overall tortuosity score per subject will be determined by selecting the most frequent tortuosity score in the 12 studied microcirculatory imaging areas (3 microcirculatory imaging areas per quadrant).

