### 9.3 Other study parameters

Demographic data and other baseline characteristics will be summarised using descriptive statistics. The main analyses will also be performed in a priori defined subgroup analyses such as age at baseline, smokers vs non-smokers ect.

Additional explorative analyses involve the analysis of prognostic and predictive factors for achieving the primary or secondary endpoint, this will be investigated by using logistic regression. The level of significance for all tests will be set at  $p<0.05$ .

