### 10.3 Benefits and risks assessment, group relatedness

The prevalence of type 2 diabetes is high in South Asian patients [22]. These patients have a 40 times higher risk of developing ESRD and a faster progression to renal failure compared to West European patients [54]. This is may be linked to increased systemic and glomerular inflammation in these patients [24, 55, 56]. Consequently, these patients will probably have an impaired endothelial glycocalyx with high heparanase activity and would benefit the most from treatments that support the glycocalyx homeostasis and reduce inflammation burden. To date, treatments for diabetic nephropathy are insufficient in preventing the development of ESRD. The interventions in this study can be used as add-on dietary interventions to reduce residual albuminuria and progression of renal disease.

The intervention burden in the FMD arm is for 5 days a month and in the other arms by taking daily capsules. Blood and urine sampling and non-invasive SDF imaging will be done at 3 time points in all intervention groups. In addition, patients are frequently monitored due to the possible effects of the interventions on glucose levels and insulin sensitivity. For the FMD group this means frequently measuring glucose values trough a finger prick.

Patients in the diet group have a risk of the occurrence of hypoglycemia during the study. In the days of the diet, this risk is reduced by stopping the hypoglycemic drugs that can cause hypoglycemia. After the diet, patients are asked to measure their glucose levels regularly.

The dosages of the hypoglycemic drugs can be altered if needed.

Other risks of the interventions may be an allergic reaction to one of the components of the diet or the food supplement. However, if eligible patients already are known with specific food allergies, they are excluded from the study. Effects on kidney function and liver function will be monitored during the study, but are not expected as a result of the interventions. In our opinion, the risk of the interventions is reduced within our study design and therefore the limited side effects and possible beneficial effects of the interventions on metabolic parameters, microvascular health and albuminuria justify participation in this study.

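### Section 9.2 tests within-arm change in categorical outcomes with Pearson's chi-squared, although both values come from the same patients

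*Combined protocol and SAP*

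**What the plan says.** Section 9.2 (Secondary study parameters) states that categorical data are to be "tested within the group between baseline and 3 months using a Pearson's Chi-squared test". For continuous data over the same interval it uses paired methods: "A paired two-tailed Student's t test or Wilcoxon signed rank test will be used to calculate the effect within the group". For the 6-month follow-up it again names the paired t and signed rank tests, and says these tests for "differences of the primary and secondary parameters between baseline and 6 months within the group will be used to evaluate the legacy effect". That sentence makes no exception for categorical data. Section 9.1 also uses a paired t test for within-arm change in the Microvascular Health Index (MHI). No paired test for categorical data is named anywhere in section 9.

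The plan does not list its categorical outcomes. The candidates are:

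- **Capillary tortuosity** (section 7.3, SDF imaging): "The number of twists will be stratified as 0: no twists (or pinhead capillaries) to 4: four or more twists". Section 10.3 says "non-invasive SDF imaging will be done at 3 time points in all intervention groups". Tortuosity is not listed as an endpoint in section 7.1.
- **Urinary heparan sulfate (HS) domains.** One secondary objective in section 2 is "Reduce occurrence of specific urinary HS domains", which could mean present or absent. The Urine collection text in section 7.3 says "Levels of creatinine, albumin, heparanase, MCP-1 and HS-fragments will be measured in the urine samples", which points to a continuous measure.
- **EQ-5D-5L dimensions and urine dipstick results** (section 7.3). Neither is listed as an endpoint in section 7.1.

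**The concern.** Pearson's chi-squared test of two proportions assumes independent groups. Here each patient contributes a baseline and a 3-month value, and the table can be built in only two ways.

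- **Visit by category.** The visits are stacked as if they were two separate samples. When a patient's two values are positively correlated, the assumed variance of the difference is too large and the test becomes conservative.
- **Baseline category by 3-month category.** The test asks whether baseline status predicts 3-month status. For a stable trait it usually does, so the test rejects often when nothing has changed.

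Section 9.2 is also uneven. Taken literally, a categorical secondary outcome gets an unpaired test at 3 months and a paired one at 6 months. For any outcome analysed in categories, the reported within-arm p-value would not measure change, and the direction of the error depends on a layout that the plan leaves open.

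**Working it through.** **Inputs.** From section 4.4: 23 evaluable patients per arm (30 enrolled), MHI difference 0.35, SD 0.41, two-sided alpha 0.05. Section 9.3 sets p<0.05 for all tests. The documents give no category proportions and no within-patient correlations, so those below are assumptions shown over a range.

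**The plan's own figure.** The standardised difference is 0.35/0.41 = 0.854. A two-sample t test at 80% power needs n = 22.54, so 23 per group, with power 0.808. The plan's 23 is reproduced. It rests on the MHI t test and does not depend on this point; it only supplies n for what follows.

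**Why stacking is conservative.** With proportion p at both visits and correlation phi, the variance of the difference in proportions is 2p(1−p)(1−phi)/n. Stacked Pearson uses 2p(1−p)/n. The large-sample size of a nominal 5% test is therefore 2[1 − Φ(1.96/√(1−phi))], which is 5.0, 1.9 and 0.6% at phi 0, 0.3 and 0.5.

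**Binary outcome, n = 23, exact enumeration, no continuity correction.**

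Rejection rate with 50% at both visits (no change):

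| Test | phi 0 | phi 0.3 | phi 0.5 |
|---|---|---|---|
| Pearson, stacked | 0.054 | 0.021 | 0.007 |
| Pearson, cross-table | 0.052 | 0.298 | 0.690 |
| McNemar, asymptotic | 0.043 | 0.044 | 0.049 |
| McNemar, mid-p | 0.042 | 0.039 | 0.030 |
| McNemar, exact | 0.024 | 0.019 | 0.012 |

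Power for a change from 60% to 35%:

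| Test | phi 0 | phi 0.3 | phi 0.5 |
|---|---|---|---|
| Pearson, stacked | 0.415 | 0.394 | 0.369 |
| McNemar, asymptotic | 0.360 | 0.487 | 0.679 |
| McNemar, mid-p | 0.360 | 0.479 | 0.617 |
| McNemar, exact | 0.275 | 0.368 | 0.468 |

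**Five-level ordered score (as for tortuosity), n = 23.** 100,000 simulated trials per cell; a latent bivariate normal is cut to give 10/25/30/25/10% at baseline. The change is a fall of 0.5 latent SD, to about 22/33/27/15/4%.

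| Quantity | rho 0 | 0.3 | 0.5 | 0.7 |
|---|---|---|---|---|
| No change: Pearson, stacked | 0.042 | 0.032 | 0.024 | 0.014 |
| No change: Pearson, cross-table | 0.044 | 0.081 | 0.185 | 0.471 |
| No change: Wilcoxon signed rank | 0.049 | 0.049 | 0.049 | 0.047 |
| Power: Pearson, stacked | 0.175 | 0.145 | 0.118 | 0.089 |
| Power: Wilcoxon signed rank | 0.333 | 0.432 | 0.546 | 0.736 |

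The advantage at rho 0 cannot come from pairing. It arises because Pearson ignores the order of the categories. The ranking also holds from a uniform baseline (Pearson 0.191 down to 0.107, Wilcoxon 0.323 up to 0.707) and from a skewed one of 60/20/12/6/2% (Pearson 0.111 down to 0.065, Wilcoxon 0.239 up to 0.460).

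**Two tables of 23 patients** (positive at both visits / positive to negative / negative to positive / negative at both).

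- 8/6/0/9: positives fall from 14 to 8. Stacked Pearson: 46(14×15 − 9×8)²/(23×23×22×24) = 3.14, p = 0.077. Exact McNemar: 2 × 0.5⁶, p = 0.031. The conclusion differs.
- 10/2/2/9: no net change. Stacked Pearson and exact McNemar both give p = 1.0. Cross-table Pearson: 23(10×9 − 2×2)²/(12×11×12×11) = 9.76, p = 0.002.

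**The case against.** The case for leaving this as a minor wording matter has four parts.

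**Reach.** No endpoint in section 7.1 is shown to fall under the rule. Nearly all are plainly continuous, HS fragments appear to be measured as levels, and tortuosity, EQ-5D-5L and dipstick results are not endpoints. A team analysing tortuosity might well use the signed rank test that section 9.2 already names. This stands as a limit on impact. But section 9.2 contains a rule for categorical data, does not say what it covers, and the HS objective is worded as occurrence.

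**Consistency.** The 6-month sentence may simply have continuous parameters in mind, in which case there is no contradiction. That reading is possible. The literal one is supported by the absence of any exception, and the 3-month error does not depend on it.

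**Size.** The highest rejection rates (47% and 69%) need the cross-table layout, which the plan does not specify, and every proportion and correlation is assumed. This is correct. In the stacked layout the cost is mainly lost power.

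**The remedy.** For binary data, exact McNemar has less power than stacked Pearson at phi 0 (0.275 against 0.415) and at phi 0.3 (0.368 against 0.394). This also stands. At phi 0 stacked Pearson beats every McNemar version. The argument for binary outcomes is chiefly validity, with a clear gain in power across versions only at phi 0.5.

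**Conclusion.** The concern holds. As written, the 3-month within-arm rule for categorical data is not a valid test of change in either layout. It should be corrected, although its reach is small: the primary analysis, the sample size and the randomised between-arm comparisons are untouched, as are nearly all listed secondary endpoints.

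Where it applies, the effect is material. With no change and correlation of 0.5 or above, stacked Pearson rejects in 0.7% (binary, phi 0.5) to 2.4% (five-level, rho 0.5) of trials, and cross-table Pearson in 18.5% (five-level, rho 0.5) to 69.0% (binary, phi 0.5). For an ordered five-level score, the signed rank test has about twice the power of stacked Pearson at rho 0 (0.333 against 0.175) and about eight times at rho 0.7 (0.736 against 0.089). These sizes rest on 23 patients per arm and on assumed distributions and correlations. That the test is wrong for paired data does not depend on them.

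**What to change.** In section 9.2, replace Pearson's chi-squared for within-arm change, at 3 and at 6 months, with:

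- McNemar's test for binary outcomes, stating the version;
- the Wilcoxon signed rank test for ordered scores such as tortuosity;
- a marginal homogeneity test for more than two unordered categories.

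On the McNemar version: in the examples above the exact form has a type I error of 1.2 to 2.4% and can have less power than Pearson when within-patient correlation is low. The mid-p form (3.0 to 4.2%) reduces this.

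List the categorical outcomes, and say whether HS domains are scored as present or absent and whether tortuosity is to be analysed.

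As a clarification only, name chi-squared or Fisher's exact test for diet against placebo and supplement against placebo on binary or nominal outcomes. Section 9.2 names no such test, and the logistic regression in section 9.3 ("this will be investigated by using logistic regression") is exploratory. For binary outcomes little turns on this: at 23 per arm the squared Mann-Whitney statistic is 45/46 of chi-squared, and for 60% against 35% both have power 0.415 (Fisher 0.301).

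The cost is one or two sentences plus a short list of outcomes. It needs no new data and does not change the sample size.

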#### **4.4 Sample size calculation**

The primary outcome will be improvement of the Microvascular Health Index after 3 months. The sample size is chosen according to a pilot study with 13 healthy volunteers receiving the food supplement Endocalyx™ for 3 consecutive months. After 3 months, a 31% improvement in Microvascular Health Index was demonstrated, expressed in a significant increase of the MHI from 1.05 at baseline, to 1.38 at 3 months (improvement of 0.33).

Group sample sizes of 23 per group achieve 80% power to detect a difference of 0.35 between the null hypothesis that group improvement means are 0.0 and the alternative hypothesis that the improvement mean of group 2 or 3 is 0.35 with estimated group standard deviations of 0.41 with a significance level (alpha) of 0.05000 using a two-sided two-sample t-test. If we anticipate a 25% drop out rate per group, we will need 30 patients per group.

Therefore, we decided to enrol a total number of 90 patients in this study.

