#### 7.1.2 Secondary study parameters/endpoints

Secondary endpoints include;

- Albuminuria: urinary excretion of albumin, using albumin/creatinine ratio in mg/mmol.
- Inflammation: urinary heparanase and MCP-1 expression, serum C-reactive protein, and MCP-1 levels.
- Metabolic response: fasting glucose, HbA1c, C-peptide, IGF-1, total cholesterol, LDL cholesterol, HDL cholesterol, triglycerides levels, body weight, waist circumference, waist-to-hip ratio and systolic blood pressure.
- Identifying specific urinary heparan sulfate domains.

To evaluate the legacy effects of the interventions, the primary and secondary parameters will also be assed three months after stopping the intervention.

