## 9. STATISTICAL ANALYSIS

### 9.1 Primary study parameter

SPSS will be used for all statistical analysis. Data analysis will be performed based on the intention to treat principle. Patients will be included in the analyses according to the treatment to which they were randomised.

The primary endpoint Microvascular Health index (MHI) will be summarized in mean with standard deviation or median with interquartile range. The effect within the group between baseline and 3 months is tested using a paired Student's t test (two-tailed). Differences in improvement of the MHI between baseline and 3 months between the FMD group and the placebo group and the food supplement and placebo group will be tested with an independent Student's t test.

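### Section 9.2 does not say what quantity is compared with placebo for the secondary endpoints; adjusting for the baseline value would settle this and beat either reading on precision

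*Combined protocol and SAP*

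**What the plan says.** Section 2 introduces the secondary objectives with "If the fasting mimicking diet and the food supplement after 3 months can" and then lists aims worded as decreasing, reducing or improving the parameters. Section 7.1.2 lists the parameters themselves, for example "Metabolic response: fasting glucose, HbA1c, C-peptide, IGF-1, total cholesterol, LDL cholesterol, HDL cholesterol, triglycerides levels, body weight, waist circumference, waist-to-hip ratio and systolic blood pressure", without saying whether the endpoint is a change or a 3-month value.

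Section 9.2 gives two analyses at 3 months for continuous secondary data. Within each arm, a paired t or signed rank test "will be used to calculate the effect within the group between baseline and 3 months". Between arms, "Differences in outcomes between the groups (diet vs placebo and supplement vs placebo) will be tested with a Student's t test for normally distributed data"; where the data are not normal, a Mann-Whitney test takes its place.

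Section 9.1 is more exact about the primary endpoint. The comparison is on "Differences in improvement of the MHI between baseline and 3 months between the FMD group and the placebo group", and likewise for the supplement. Baseline adjustment is mentioned nowhere in the document.

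**The concern.** The comparison with placebo is the only randomised evidence on the secondary endpoints, and it is the one whose quantity is not stated. The uncontrolled within-arm test is fully specified.

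Two analysts following section 9.2 could reasonably test 3-month values or changes from baseline. They would get different estimates, standard errors and p values from the same data, and the choice could be made after seeing them. Neither reading makes the best use of the T0 value, which is already collected for most of these parameters (sections 7.3 and its laboratory paragraph: bloods at T0, T4 and T5; weight, waist and blood pressure at T0 and T4). Precision matters in a trial with about 23 evaluable patients per arm.

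**Working it through.** **The plan's own figure.** Section 4.4 states: "Group sample sizes of 23 per group achieve 80% power to detect a difference of 0.35", with SD 0.41 and two-sided alpha 0.05. The standardised effect is 0.35/0.41 = 0.854. The exact noncentral t calculation gives 79.0% power at 22 per arm and 80.8% at 23, so 23 reproduces. It concerns improvement in MHI only; no power is stated for any secondary endpoint.

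**Inputs for the comparison.** 23 per arm (section 4.4) and two-sided 0.05 (sections 4.4 and 9.3). The baseline to 3-month correlation r is an assumption, because the documents give neither r nor an SD for any secondary endpoint. I also assume the same between-person SD, σ, at both times and in both arms.

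**Per-patient variance behind each between-arm test**
- 3-month values: σ²
- change from baseline: 2σ²(1−r)
- 3-month value adjusted for baseline (ANCOVA): σ²(1−r²)

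The variance ratio of 3-month values to adjusted is 1/(1−r²). The ratio of change to adjusted is 2σ²(1−r)/[σ²(1−r)(1+r)] = 2/(1+r). Both exceed 1 for any r strictly between 0 and 1. 3-month values and change scores tie at r=0.5.

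**Power.** With 23 per arm, 80% power needs a standardised difference of 0.845. For each r, take the effect that the adjusted test detects with 80% power, 0.845·√(1−r²)·σ, and recompute the power of the other two tests.

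Example, r=0.8: √(1−0.64) = 0.6, so the effect is 0.845 × 0.6 = 0.507σ. On 3-month values the standardised effect is 0.507, which gives 39% power. On change the SD is √(2×0.2)σ = 0.632σ, so the standardised effect is 0.507/0.632 = 0.80, which gives 76% power.

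| Assumed r | Variance, 3-month ÷ adjusted | Variance, change ÷ adjusted | Power, adjusted | Power, 3-month values | Power, change |
|---|---|---|---|---|---|
| 0.3 | 1.10 | 1.54 | 80% | 76% | 62% |
| 0.5 | 1.33 | 1.33 | 80% | 68% | 68% |
| 0.7 | 1.96 | 1.18 | 80% | 52% | 73% |
| 0.8 | 2.78 | 1.11 | 80% | 39% | 76% |
| 0.9 | 5.26 | 1.05 | 80% | 23% | 78% |

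With 30 per arm the powers agree to within a percentage point. The table ignores the single degree of freedom spent on the covariate (44 becomes 43).

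**Where more than half the power is lost.** On 3-month values, power falls below 40% once r exceeds about 0.79 when adjusted power is 80%, and once r exceeds about 0.81 when change-score power is 80%.

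**The case against.** The strongest reply is that section 9.2 means change. It has the same structure as section 9.1, a paired within-arm test followed by a comparison with placebo, and in 9.1 the second step is explicitly on improvement. The objectives are also about reduction and improvement. On that reading nothing is lost relative to a change score. This stands as far as it goes: a reader might infer that section 9.2 prescribes a test of raw 3-month values, but the sentence names no time point and does not say so. The defect is an undefined quantity.

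A reader might also infer that most of the power is lost. That needs both the 3-month reading and r of about 0.8 or more. Such an r is plausible for body weight or waist, but the documents do not show it for any endpoint. It should not be presumed for CRP, MCP-1, heparanase or albumin/creatinine ratio. Below r=0.5, 3-month values are more precise than change scores.

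A third tempting inference is that a significant within-arm fall beside a null placebo comparison would be an artefact of testing different quantities. It can arise anyway. With 23 per arm and a true change of 0.5 SD of change in one arm only, the paired test has 63% power and the between-arm test on change 38%. Adjustment will not abolish that pattern.

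Finally, choosing ANCOVA over change is a matter of efficiency, and no secondary endpoint is powered. Both statements are true. They limit the weight of the point, but they do not remove the ambiguity or the gain in precision.

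**Conclusion.** The point holds as a gap in specification together with an avoidable loss of precision. It is not a point about bias, since both readings are unbiased under randomisation, and no stated power figure is affected.

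For an effect that the adjusted test would detect with 80% power, over assumed r from 0.3 to 0.9 the 3-month reading gives about 76% down to 23%, and the change reading about 62% up to 78%. So the cost is small for 3-month values at low r and for change scores at high r. It is large only for 3-month values of highly stable traits. These figures rest on equal variances at the two times and on a correlation that the documents do not supply. The ordering does not depend on which r is right: under that model, for any positive r below 1, adjustment is more precise than either reading, apart from the one degree of freedom.

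**What to change.** Replace the between-group sentence in section 9.2. For each continuous secondary parameter measured at T0, compare each intervention with placebo at T4 using a linear model (ANCOVA) with treatment arm and the parameter's own T0 value as covariate. Analyse skewed parameters on the log scale, with T0 logged too, and name in advance which these are. Report the adjusted mean difference, or ratio for logged parameters, with its 95% CI.

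If the team prefers to stay with simple two-sample tests, the minimum is to state the quantity and the time point as section 9.1 does, that is, change from baseline to 3 months. That removes the ambiguity but gives up precision, most of all for markers with low r.

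The cost of the main fix is one sentence, one degree of freedom per model and slightly more analysis work in SPSS. It needs no new data, visits or patients, and leaves the sample size unchanged.

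### Section 9.2 analyses continuous secondary endpoints on the raw scale, with the test chosen from the observed distribution and no planned between-group estimate; a log-scale ANCOVA fixed in advance would use the same data better.

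*Combined protocol and SAP*

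**What the plan says.** Section 9.2 compares diet with placebo and supplement with placebo using a test that depends on the data: differences "will be tested with a Student's t test for normally distributed data or Mann-Whitney" U "test for non-normally distributed data". The quantity compared is given only as "Differences in outcomes between the groups (diet vs placebo and supplement vs placebo"), without saying whether this means change from baseline or the 3-month value. Summaries follow the same split: "The continuous data will be summarized in mean with standard deviation in case of normal distribution or median with interquartile range" otherwise. Within groups, "A paired two-tailed Student's t test or Wilcoxon signed rank test will be used to calculate the effect within the group", again without a rule for choosing.

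The section does not say how normality is judged, or whether per arm, per contrast or per endpoint. It names no transformation, baseline adjustment, between-group estimate or confidence interval. By contrast, section 9.1 fixes the test for the primary endpoint: the difference in improvement "will be tested with an independent Student's t test".

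The endpoints affected are in section 7.1.2. They include "Albuminuria: urinary excretion of albumin, using albumin/creatinine ratio in mg/mmol" and "Inflammation: urinary heparanase and MCP-1 expression, serum C-reactive protein, and MCP-1 levels".

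**The concern.** Several of these endpoints are positive concentrations or ratios for which right skew and proportional change are plausible. The clearest case in the documents is the albumin/creatinine ratio: section 4.2 admits 0.3 to below 30 mg/mmol, a 30/0.3 = 100-fold range. If a marker changes proportionally, the raw change depends on where each patient started, which adds spread unrelated to treatment.

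The inflammation markers test the rationale in section 1, and both interventions are judged against one placebo arm. At stake are the power to see an effect on these markers and a common effect measure for reading the two contrasts side by side. A Mann-Whitney p-value with group medians and interquartile ranges does not supply that measure.

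**Working it through.** **The plan's own figure.** Section 4.4 gives 23 completers per group for 80% power (difference 0.35, SD 0.41, two-sided 0.05). Standardised difference 0.35/0.41 = 0.854; noncentrality 0.854 × √(23/2) = 2.895; power with 44 df = 80.8% (79.0% at 22 per group). The 23 is reproduced. No power is stated for any secondary endpoint.

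**Inputs.** From the documents: 23 per arm and two-sided 0.05 (section 4.4; section 9.3 sets 0.05 for all tests). Assumed: log-normal marker; log SD s = 0.5, 0.7 or 1.0; baseline to 3-month correlation r = 0.7; true reduction 30%, so the log effect is ln 0.7 = −0.357; normality judged by Shapiro-Wilk at 0.05 in each arm.

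**Log-scale analyses in closed form.** Noncentrality = 0.357/SD × √(23/2), where SD = s√(2(1−r)) for the t test on log change and s√(1−r²) for ANCOVA.

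| s | SD, log change | noncentrality | power | SD, ANCOVA | noncentrality | power |
|---|---|---|---|---|---|---|
| 0.5 | 0.387 | 3.12 | 86% | 0.357 | 3.39 | 91% |
| 0.7 | 0.542 | 2.23 | 59% | 0.500 | 2.42 | 66% |
| 1.0 | 0.775 | 1.56 | 33% | 0.714 | 1.69 | 38% |

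**Simulation of the section 9.2 rule, same settings.** Repeat runs differ by up to about 3 points.

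| Analysis | s = 0.5 | s = 0.7 | s = 1.0 |
|---|---|---|---|
| Raw change, t test always | 70% | 39% | 19% |
| Raw change, section 9.2 rule | 73% | 44% | 27% |
| 3-month values, section 9.2 rule | 65% | 36% | 20% |
| Log change, Mann-Whitney | 84% | 57% | 32% |
| Log change, t test | 86% | 60% | 36% |
| Log-scale ANCOVA | 92% | 65% | 39% |

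**Where the loss arises.**
- The switch: the rule beats the raw t test by 3, 5 and 8 points (73−70, 44−39, 27−19), so it gains power.
- The rank test: on log change it trails the t test by only 2 to 4 points.
- The scale: moving from the rule on raw change to a t test on log change gains 13, 16 and 9 points; ANCOVA adds a further 6, 5 and 3.
- If 3-month values are meant, ranks are unchanged by taking logs, so scale matters little. A log-scale t test without baseline has noncentrality 0.357/s × √(23/2) = 2.42, 1.73 and 1.21, power 66/39/22%, close to the rule's 65/36/20%. The loss of 27, 29 and 19 points against ANCOVA comes almost wholly from not using baseline.

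**Type I error.** In null simulations the rule rejected in 4.4 to 6.2% of trials.

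**Different tests in the two contrasts.** If normality is judged per contrast, this occurs on change in roughly 20 to 35% of trials at log SD 0.3 to 0.7 and about 10% at 1.0. On 3-month values it is about 20 to 30% at 0.3 to 0.5 and under 1% at 1.0. If judged once per endpoint, it cannot occur.

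**Low correlation.** At r = 0.3 and s = 0.5, a t test on log change has about 51% power, below the rule on 3-month values (64%). ANCOVA has SD 0.5 × √(1−0.09) = 0.477, noncentrality 2.54 and power 70%. Baseline adjustment is therefore the safer replacement.

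**The case against.** The strongest reply is that the comparison favours the log scale by construction: data simulated as log-normal with a proportional effect suit a log-scale model. The documents give no SD, skew, correlation or expected effect for any secondary marker. This stands, so the power figures are conditional illustrations. They also depend on the effect: at log SD 0.3 a 30% reduction is detected almost always by any of these methods.

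A second reply is that choosing a rank test for skewed data is ordinary practice and does no harm to validity. That also stands. A reader might infer that the switch, or Mann-Whitney, is what costs skewed markers their power, or that choosing after seeing the data inflates false positives. The calculations support neither.

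A third reply is that the missing effect size is not special to the rank branch, since section 9.2 plans no between-group estimate or interval on the t branch either. This is correct. The difference is one of degree: a mean difference follows directly from the planned group means, whereas no between-group effect follows from medians and interquartile ranges. The gap therefore covers all continuous secondary endpoints.

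Finally, the text does not say that normality is judged per contrast. A reader might infer that the two contrasts will be tested differently; the wording only fails to exclude it.

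**Conclusion.** The point holds as a cheap improvement to the secondary analyses. The rule leaves the scale, the normality criterion and the effect measure open, and under the stated assumptions it gives up power that a fixed analysis would recover: 19, 21 and 12 points on raw change (92−73, 65−44, 39−27), and more on 3-month values. These sizes rest on log-normality, proportional effects, the assumed log SDs and the correlation of 0.7. The case for a fixed scale, one model for both contrasts and an interval estimate does not depend on the exact figures. The primary test is fixed in section 9.1 and is not touched.

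**What to change.** Rewrite section 9.2 before any outcome data are examined by arm. Unblinding is not a usable cut-off, because only the supplement and placebo arms are blinded (section 7.2).

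- Fix the scale per endpoint. Log: albumin/creatinine ratio, CRP, serum and urinary MCP-1, urinary heparanase and triglycerides, with a stated rule for undetectable values. Raw: body measures, blood pressure, HbA1c and cholesterol. Assign the rest (fasting glucose, C-peptide, IGF-1, heparan sulfate domains) at the same time.
- Analyse both placebo contrasts with the same model: ANCOVA of the 3-month value on arm and baseline, on that scale.
- Report geometric mean ratios (log) or mean differences (raw) with 95% CI.
- Keep the rank tests as a sensitivity analysis.

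The baseline and 3-month samples are already planned (section 7.3), so no extra data are needed. The cost is a wording amendment to section 9.2, and skewed markers will be reported as ratios, which some readers find less familiar than medians.
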